Statistical Considerations:	
Diese Studie ist eine Beobachtungstudie mit zu erwartenden deskriptiven Ergebnissen.
 
Die Studie wird gepowert für den primären Endpunkt, der mittleren Veränderung des Blut-Copeptins in den ersten 48 Stunden nach Aufnahme auf die Intensivstation bei kritisch kranken Kindern und Jugendlichen.
 
Folgende Faktoren sind dabei zu berücksichtigen:
 
 
• Basierend auf den verfügbaren publizierten Daten wird bei 48 Stunden eine mittlere Copeptin-Differenz (zum Aufnahmezeitpunkt; d) von 0.3 ng/ml (Inter-Quartilbereich: 1.1 ng/ml) erwartet. Daraus ergeben sich die Standardabweichung (sd) von 0.82 ng/ml und die Effektstärke (d/sd) von 0.36.
 
• 60% der Patienten werden potentiell innert 48 Stunden verlegt.
 
• 90% der gewonnenen Werte liegen im messbaren Bereich.
 
• Mit den Voraussetzungen 0.8 Power, Signifikanzniveau 0.05, Effektstärke 0.36, 60 % Drop-out, 10% außerhalb des messbaren Bereichs errechnet sich eine Patientenzahl von 170 Patienten.
 

Other methodological Considerations:	Alle eingeschlossenen Patienten werden in die Analyse für den primären Endpunkt aufgenommen. 60% der Patienten der Intensivstation werden innert 48 Stunden verlegt, daher muss die Patientenzahl entsprechend erhöht werden. Von besonderem Interesse sind darüber hinaus die Patienten, die länger als 48 Stunden hospitalisiert bleiben, dies sind in der Regel schwer kranke Patienten. Daher werden zunächst die Blut- Copeptin-Werte aller eingeschlossenen Patienten innert den ersten 48 Stunden analysiert und in einem zweiten Schritt die Copeptin-Werte der Patienten analysiert, die bis zu 7 Tagen bleiben (13% aller Patienten bleiben länger als 7 Tage auf der Intensivstation des Kinderspital hospitalisiert).

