### **8.2.2 Handling of missing data**

#### **Primary outcome:**

Missing blood copeptin and/or blood pressure data is expected to occur at time points after baseline assessment because of the following reasons:

- Transfer to another unit (mainly associated with improvement of patient condition)
- Death (associated with worsening of patient condition)

Missing copeptin and/or blood pressure data may occur at any time point because of the following reasons:

- Measurement below the limit of quantification of the analytical method (only copeptin)
- Technical difficulties in blood sampling and/or blood pressure measurement
- Consent withdrawal

The remaining covariates, including age and medical condition (including septic shock, heart failure, traumatic head injury, brain tumor and/or intracranial operation, perinatal asphyxia and severity of disease) are unlikely to be missing since they are assessed at ICU admission and included in the electronic patient record.

For the initial assessment of blood copeptin kinetics, all individual data independent of later missing blood copeptin measurements will be included in the analysis (“full analysis”, i.e. according to the intention-to-treat principle). One advantage of the planned mixed-effect modelling is that it can indeed handle unbalanced individual data. Measurements below the limit of quantification will not be omitted but included as censored measurements. Missing covariates at specific time points (age, blood pressure) will be imputed or interpolated based on other observed individual data (e.g. based on previous and/or subsequent assessments).

In a sensitivity analysis, the time-course of only complete patient data over 7 days (“complete case analysis”, i.e. per protocol) will be compared with the “full analysis set” and model parameters will be assessed for a bias induced by potentially copeptin-dependent (i.e. non-random) missingness reasons.

If a bias is suggested we will furthermore investigate the time-course of copeptin in patients with missing data, stratified for different reasons of missingness (“stratified sub-analyses”).

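### The comparison with 7-day completers cannot show whether missing data bias the copeptin model, yet it is the plan's only such check and the gate to further work

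*Protocol*

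**What the plan says.** Section 8.2.2 of the protocol (primary outcome) keeps every child in the kinetic model, treats values below the limit of quantification as censored, and notes in its favour: "One advantage of the planned mixed-effect modelling is that it can indeed handle unbalanced individual data".

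The sensitivity analysis takes "the time-course of only complete patient data over 7 days" and compares it with the full analysis set. Its stated purpose is that "model parameters will be assessed for a bias induced by potentially copeptin-dependent (i.e. non-random) missingness reasons".

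What follows is conditional: "If a bias is suggested we will furthermore investigate the time-course of copeptin in patients with missing data", stratified by the reason for missingness.

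The same section links transfer mainly to improvement and death to worsening. The Synopsis (other methodological considerations) says "13% aller Patienten bleiben länger als 7 Tage", that is, 13% of all patients stay longer than 7 days. Section 5.2 says that children who stay beyond 48 hours are generally the more severely ill.

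**The concern.** The question put is whether the full-set model is biased by missingness that depends on copeptin. The comparison answers a different one: do children who stay a week have the same copeptin parameters as all children? Sampling stops at ICU discharge or death, so the completers are long-stayers by construction, and on the protocol's own account a selected group.

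The wording also treats dependence on copeptin as the same thing as non-random missingness. Only dependence on copeptin that was not observed, given what was observed and the covariates in the model, biases a correctly specified likelihood model.

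Two things are at stake. A sound 7-day course may be reported as suspect. A biased one may be reported as checked, in which case the stratified sub-analyses are never triggered. The model then feeds the simulated proportions below the 1.12 ng/mL cut-off and the individual parameters used as outcome predictors (section 8.2.1).

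**Working it through.** **Inputs from the protocol.** N = 170 (section 8.1: 62 × 2.5 × 1.1 = 170.5, given as 170); 13% stay beyond 7 days (Synopsis); 37.7% stay beyond 48 hours (section 5.2); sampling ends at discharge or death (sections 5.2, 6.3); samples are taken only alongside medically indicated draws (section 5.2). **Assumed, because the protocol gives no values:** copeptin variances, the share remaining at 12, 24 and 96 hours, exit mechanisms and strengths, and the decision rule.

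**Step 1, the reference group.** 0.13 × 170 = 22.1 children, against 0.377 × 170 = 64.1 still present at 48 hours. About 22 is an upper figure, since each child also needs all six samples.

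**Step 2, what each fit requires.** Let y be a child's copeptin course, x the model covariates and r the time of exit.

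- Full set: the likelihood is ∫ f(y_obs, y_mis | x) P(r | y_obs, y_mis, x) dy_mis. If P(r | y_obs, y_mis, x) = P(r | y_obs, x), that factor leaves the integral and f(y_obs | x) alone gives valid estimates.
- Completers: f(y | stay to day 7, x) = f(y | x) × P(stay | y, x) / P(stay | x). This equals f(y | x) only if staying is unrelated to copeptin given x.

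So if exit depends on observed copeptin, the full-set fit is valid and the completers' fit is not. If exit depends only on covariates in the model, both are valid. If exit depends on unobserved copeptin, both are biased, and their difference does not measure the bias of either.

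**Step 3, illustration A.** Log copeptin = b0 + b1·t + e, with SDs 0.6, 0.15 per day and 0.35; true mean slope 0; N = 170; 86/60/38/22/13% remaining at 12/24/48/96/168 hours. A flag means the full-set intercept or slope lies outside the completers' 95% CI. There are 200 to 300 studies per cell. Triples are weak/moderate/strong dependence (log-odds 0.4/0.8/1.5; the last row uses a different scale).

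| Exit depends on | Full-set slope error per day (coverage) | Flagged |
|---|---|---|
| nothing related to copeptin | none by construction | 7% |
| baseline severity, in the model | unbiased | 8/10/12% |
| baseline severity, left out of the model | +0.002 to +0.006 (90–94%) | 37/80/98% |
| last measured copeptin | 0.000 to +0.002 (95–96%) | 48/96/100% |
| child's true level at last visit | +0.010/+0.027/+0.043 (90/75/52%) | 40/94/100% |
| child's own unobserved slope | +0.06/+0.09/+0.12 (24/3/0%) | 22/42/58% |

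The fourth and fifth rows have nearly the same flag rates, although one model is unbiased and the other is not. The last row has the largest bias and much lower flag rates. With a Hausman-type rule the rates are 62/99/100% (last measured copeptin), 46/73/88% (own slope) and 15% (nothing related).

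**Step 4, illustration B.** A separate set-up: true intercept 1.00, true slope 0.050 per day, 400 studies per setting, 38% and 13% remaining at 48 and 168 hours. A flag is a Hausman-type difference beyond 1.96 SE in intercept or slope.

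- Exit by last observed value: full-set intercept 0.996–0.997 and slope 0.051–0.052; completers' intercept 1.37–1.58; flagged in 92–100%. Slope-interval coverage was 85–89% in the main setting, but the estimate was not shifted.
- Exit by unobserved change: full-set slope 0.104–0.141, or 2.1 to 2.8 times the truth (0.104/0.050; 0.141/0.050), coverage 0–28%. The completers' slope, 0.084–0.130, is shifted the same way. Not flagged in 44–79%. With N = 1,700 the slope itself was flagged in only 10%, since both fits carry the same error (0.101 and 0.097).
- Exit by latent slope: full-set slope 0.071–0.140; not flagged in 20–85%.
- Exit by unobserved current level: full-set slope 0.093–0.135; some parameter flagged in 79–98%, mainly the intercept, which is close to unbiased in the full set. The slope was not flagged in 45–88%.
- A mechanism that retains children with high levels and falling slopes: not flagged in 1%.

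**The case against.** The strongest counter-case has five parts.

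- **Blinding.** Clinicians do not see copeptin, and samples are assayed in batches weeks later (sections 2.4, 5.2, 5.4). Measured values cannot drive discharge directly; any link runs through clinical condition. This stands, and it makes the pure observed-copeptin scenario, the source of the highest false-flag rates, a limiting case.
- **Covariates.** The planned model carries severity, blood pressure, diagnoses and age (sections 4.1, 8.2.1). This stands too: where severity drives exit and is in the model, flags fall to 8–12%.
- **Decision rule.** The protocol sets no threshold, and a threshold may properly be left to the SAP. Its absence is not a fault. But the rule matters: under change-dependent exit in illustration B, clearance runs from 27–45% when the completers' estimate need only fall outside the full-set CI to 95–99% when the two CIs must not overlap. No threshold repairs the reference group.
- **Consequences.** A flag triggers only stratified descriptions; the full-set model is never replaced, and section 4.2 calls the primary endpoint descriptive. This limits the harm of a false flag, not of a false clearance.
- **Related analyses.** Section 8.2.1 uses individual copeptin parameters as predictors of ICU stay and survival. That shows whether exit tracks copeptin but does not adjust the mean course. The comparison of predicted with empirical proportions below the cut-off uses only children still sampled and is not aimed at missingness.

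A reader might infer that the check will usually flag a sound model and usually clear a biased one, at the simulated rates. The documents do not support that: they fix neither mechanism, covariate set nor rule, and level-dependent exit is mostly flagged. Nor do they support reading this as a fault in the full-set mixed model.

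**Conclusion.** The point holds as one of logic. A difference between the full-set fit and the 7-day completers does not show that the full-set model is biased, and agreement does not show that it is free of bias. Section 8.2.2 nevertheless makes this comparison the only test for missingness bias and the condition for going further, and its wording merges two situations that must be kept apart.

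The size cannot be fixed from the protocol. Under the rules used for the main runs, flag rates spanned 7–100% with an unbiased full-set model and 15–100% with a biased slope, so the ranges overlap almost completely. These rates are illustrative and rest on assumed variances, exit mechanisms and rules. False flags are fewer when severity is in the model; missed bias arises mainly when exit follows the child's slope or change rather than level. The validity of the full-set model also assumes that it is correctly specified. The point concerns the kinetic model, not the 48-hour t-tests. It is worth correcting before the analysis.

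**What to change.** In section 8.2.2 of the protocol, or in the SAP:

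1. Relabel the 7-day complete-case fit as a description of long-stayers, not a test of bias.
2. Define the missingness of concern as dependent on unobserved copeptin given the observed values and the model covariates.
3. Keep the full-set mixed model, with severity and the other listed covariates, as the main analysis under missing at random.
4. Run one sensitivity analysis for non-random exit unconditionally, for example a joint model of copeptin with shared random effects and with ICU discharge and death as separate exit types. Report how far the mean course and the proportion below the cut-off move.
5. If a delta adjustment is used instead, apply it only to discharged survivors, not after death, and say that it concerns copeptin beyond the ICU stay.

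The cost is a few sentences and some extra modelling. R and NONMEM are already named in section 8.2.1, and no new data are needed. The downside is one untestable assumption, which must be stated.

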#### **Secondary outcome:**

Missing secondary outcomes (date of discharge from ICU, date of end of respiratory support, date of death) can occur because the observation period may not be long enough to observe these events. Therefore, these unobserved outcomes will be right-censored in the time-to-event analysis (i.e. censored at random).

Catecholamine prescription is part of the electronic patient record. A non-reported dose of catecholamines will therefore be handled as such.

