On admission demographic baseline data will be recorded on paper bedside case report forms as outlined in "Schedule of assessment (Flow of research project)" (i.e. age (years + months; if <28 days: postnatal days and postconceptional age), Apgar-score, arterial umbilical cord pH; diagnosis; disease-severity-scores; operation, preoperative parameters; weight; sex). Blood samples (600 µl) will be taken from all study patients on specific points of time (on admission, with 12, 24, 48, and, if still in ICU with 96, and 168 hours following admission), processed and stored at -80 °C for batch analyses later. Just before or after blood sampling the following clinical data will be recorded: arterial blood pressure; vital parameters (respiratory rate, peripheral oxygen saturation, arterial oxygen saturation, perfusion index, heart rate, peripheral pulses, capillary refill, urine output); laboratory values (sodium, potassium, calcium, chloride, troponin, creatine kinase, creatine kinase MB, pH, partial arterial oxygen pressure (PaO2), partial carbon arterial carbon dioxide pressure (PaCO2), base deficit, arterial lactate, glucose, alanine transaminase (ALT), creatinine, C-reactive protein, haemoglobin, white blood cell count, total bilirubin); neurological parameters (Glasgow Coma Scale, CT-findings (abnormal cisterns, midline shift >5mm, traumatic subarachnoidal haemorrhage, seizures, intracranial and cerebral perfusion pressure (if invasively monitored)); neonatal parameters (results of neonatal neurological imaging (cranial ultrasound and/or MRI) and performance of neonatal cooling as prevention of neurological damage). Importantly, laboratory parameters will only be assessed, if their analysis is otherwise medically indicated for limitation of blood loss and phlebotomy. As most critically ill patients have to be equipped with invasive hemodynamic monitoring allowing repetitive blood withdrawal, no additional phlebotomy should be necessary. Copeptin values will only be analysed, when the study blood sample can be taken alongside with other medically indicated blood samples.

If the study patient is discharged from the ICU, the study period ends and no further blood samples or clinical data will be taken or analysed. Length of ICU stay will be noted. Every patient will be followed by study investigators for a total of 28 days to note date of discharge from ICU, Hospital and date of death, if applicable.

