### **6.3 Criteria for withdrawal / discontinuation of participants**

For the following reasons the study period will end immediately for the included patients.

- Withdrawal of informed consent
- Discharge from Intensive Care Unit
- Death

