### 7.3 Assessment of secondary endpoint/outcome(s)

The following secondary endpoint variables will be obtained and noted on bedside paper case report forms at the scheduled time points of assessment and blood sampling:

- Discharge date from ICU as determined by the moment of decision made by treating physicians for discharge, even though immediate discharge may not be possible due to capacity reasons of the targeted peripheral ward.
- Respiratory support.
- Vasoactive Drugs.
- Serious (Adverse) Events/Death.

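### Protocol 8.2.2 right-censors unobserved ICU discharge and end of respiratory support as 'at random' and makes no provision for death, which prevents both

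*Protocol*

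**What the plan says.** - **Censoring rule.** Section 8.2.2 (Secondary outcome) covers three dates together: ICU discharge, end of respiratory support and death. It says that missing dates "can occur because the observation period may not be long enough to observe these events", names no other reason, and concludes that "these unobserved outcomes will be right-censored in the time-to-event analysis (i.e. censored at random".
- **Discharge.** Section 7.3 defines it as "Discharge date from ICU as determined by the moment of decision made by treating physicians for discharge".
- **Death.** Section 6.3 lists withdrawal of consent, ICU discharge and death under the sentence "For the following reasons the study period will end immediately for the included patients".
- **Informative missingness.** For the primary outcome, section 8.2.2 gives among the reasons for missing data "Transfer to another unit (mainly associated with improvement of patient condition" and "Death (associated with worsening of patient condition". It plans sensitivity work for the copeptin time course only.
- **Data after discharge.** Section 5.2: "If the study patient is discharged from the ICU, the study period ends and no further blood samples or clinical data will be taken". It adds: "Every patient will be followed by study investigators for a total of 28 days to note date of discharge from ICU", together with hospital discharge and death.
- **Outcomes and predictors.** Section 4.1 names length of ICU stay and length of respiratory support as outcomes, with copeptin over up to 7 days as the predictor. Section 8.2.1 (Secondary endpoints) allows measured levels, model-derived individual parameters, or both, in a time-to-event analysis.

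**The concern.** Right-censoring at the end of a fixed follow-up is sound. The difficulty is a child whose discharge is unobserved because the child died. Longer follow-up would not supply the date, so the only stated reason does not fit. Either the rule censors that child as though discharge were still to come, or there is no rule for that child. Death precludes both discharge and end of support, and the protocol itself links it to worsening. Survival is also among the outcomes that copeptin is meant to predict, so the competing event may be related to the predictor.

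At stake is the reading of the results. With deaths censored, the model estimates the rate of discharge among children still alive in the ICU. Presented as length of stay or chance of leaving alive, that rate would be misread.

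End of support carries a second problem. A child who leaves the ICU still on support drops out of observation because of the discharge, not at a fixed calendar limit.

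**Working it through.** **1. The texts side by side.** Section 7.3 makes discharge a physician's decision and section 6.3 ends the study period at death, so an ICU death yields no discharge date at any length of follow-up. Section 8.2.2 offers only short observation as the cause of a missing date. The rule therefore either takes in ICU deaths or leaves them without a rule.

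**2. Stay distribution.** The protocol states no figure for these secondary analyses, so its stay data are the inputs:
- section 5.2: 10th percentile 0.4 d, median 1.3 d, 90th percentile 9.2 d, and 62.3% under 48 h;
- synopsis: 13% beyond 7 days.

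Log-stay was interpolated through these points on the normal-quantile scale. The fit returns 0.40, 1.30 and 9.25 d, with 37.7% at or beyond 2 days and 13.0% at or beyond 7 days.

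**3. Effect of censoring deaths on live discharge.** Let L be time to discharge and D time to death. Assume they are independent and D is exponential, with its rate set so that a share m dies in the ICU by day 28. The protocol gives no cohort mortality, so m is assumed.

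- With deaths censored, 1 - KM(28) estimates P(L < 28) = 0.977.
- The probability of live discharge is CIF(28) = P(L < 28 and L < D).
- The difference is P(D < L < 28), which cannot exceed m.

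| m | CIF(28) | 1 - KM(28) | Excess, day 28 | Excess, day 7 | Time by which 75% are discharged alive (KM: 3.5 d) |
|---|---|---|---|---|---|
| 2% | 0.960 | 0.977 | 1.6 points | 0.9 | 3.6 d |
| 5% | 0.935 | 0.977 | 4.2 points | 2.2 | 3.8 d |
| 10% | 0.891 | 0.977 | 8.6 points | 4.8 | 4.2 d |

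The first excess is taken before rounding; the rounded entries give 0.977 - 0.960 = 0.017. At 5%, 1 - 0.935 - 0.05 = 0.015 remain in the ICU at day 28. A plain lognormal stay gives 1.7, 4.2 and 8.6 points. The median stay is 1.30 d by Kaplan-Meier. Even at 20% mortality, which nothing in the protocol suggests, it moves only to 1.46 d.

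**4. End of support.** If support lasts 25 to 75% of the stay and all deaths occur on support (both assumed), the day-28 excess is 1.7-1.9, 4.4-4.9 and 8.9-9.8 points at the same three mortalities. This covers death only. The protocol does not say how many children leave the ICU on support, so that part cannot be sized.

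**5. Secondary note: the predictor.** Sampling stops at discharge, so stay fixes how many copeptin values exist: about 170 x 0.377 = 64 children can give a 48 h sample and 170 x 0.13 = 22 a 168 h sample. Null studies were simulated with n = 170, total SD 0.82 ng/mL, a between-patient variance share of 25-75%, and a Cox score test on stay. They rejected at the 5% level as follows:
- whole-stay maximum: 54-98% with a flat course;
- whole-stay mean: 6% with a flat course, 47-73% with the Table 2 rise, 61-84% with an assumed fall;
- last value: 5-6% flat, 99.8-100% with the rise, 100% with the fall;
- maximum under an assumed steep fall: 5-15%;
- admission value, 24 h and 48 h landmarks, and time-dependent last value: 4-6%;
- mixed-model random intercept: 2-5%.

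Which whole-stay summary fails thus depends on the course. The admission, landmark, time-dependent and model-derived forms were not materially inflated.

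**The case against.** The strongest reply is that section 8.2.2 never says that deaths are censored. It speaks of follow-up that is too short, which is administrative censoring and sound. Section 4.2 records stay in hours and death separately, so counting stay up to death is equally open. That stands: censoring of deaths follows from applying the rule as written, not from an express statement. It leaves the protocol with an assumption of random censoring and no rule for the case that most clearly breaks it.

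It also stands that no Kaplan-Meier curve of discharge is planned, that a cause-specific hazard remains valid with deaths censored, and that the median barely moves. A reader might infer that the planned time-to-event models are invalid. The documents do not support that; what fails is reading them as length of stay or chance of live discharge.

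The remark that transfer reflects improvement was made about missing copeptin and blood pressure, not about respiratory support. It still describes the same event, leaving the unit, which ends observation of support.

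On the predictor, a reader might infer that the window is unlimited, or that the protocol plans an analysis sure to give a spurious association. Neither is supported. The window is capped at 168 h, no whole-stay mean, last or maximum is named, and the exact form of a predictor is commonly left to the analysis plan. The one derived form that is named, model-derived individual parameters, was not inflated in the random-intercept check.

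**Conclusion.** The point holds for the censoring rule. Section 8.2.2 attributes every unobserved discharge or end of support to short follow-up, calls the censoring random and omits death, while sections 6.3 and 7.3 make death a case in which these dates never arise. At assumed ICU mortality of 2, 5 and 10%, a live-discharge probability read from the censored analysis would be about 1.6, 4.2 and 8.6 points too high at day 28. These sizes rest on the assumed mortality, on independent discharge and death times, and on the fitted stay distribution; they show direction and range, not the bias in this study. The gap for children who leave on support is real but of unknown size.

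The predictor is a secondary note only. All of this concerns exploratory secondary analyses. Nothing here bears on the primary endpoint or on N = 170.

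**What to change.** In section 8.2.2 (Secondary outcome):
1. Limit the independent-censoring statement to the administrative end of follow-up, which is day 28 for ICU discharge and death.
2. Treat death as a competing event for live ICU discharge and for end of respiratory support, and report cumulative incidence alongside cause-specific hazards.
3. State when observation of respiratory support ends, given that clinical data stop at ICU discharge, and how a child who leaves the ICU on support is counted.

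In section 8.2.1 or the analysis plan, add that copeptin measured after admission enters the stay and support models as a time-dependent covariate, in a landmark analysis or through the planned model-derived parameters, and not as a whole-stay mean, last or maximum value. This keeps the 7-day objective.

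The cost is wording and a little extra analysis. Dates of ICU discharge and death are already noted to day 28. A landmark analysis uses fewer children: about 97 to 104 of 170 at 24 h, depending on the stay fit, and about 64 at 48 h.
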